Adverse outcomes	Primary outcome	HIRA Database	
The following known treatment related outcomes will be operationally defined by KCD-7 diagnosis codes and/or NHI procedure codes in medical claims
 
 - GI bleeding I850, I883, K2211, K226, K228, K250, K252, K254, K256, K260, K262, K264, K266, K270, K272, K274, K276, K280, K282, K284, K286, K290, K3181, K5521, K625, K920, K921, K922 - Fractures S02, S12, S22, S32, S42, S52, S62, S72, S82, S92, T02, T08, T10, T12, T14.2 - Falls W00-W19 - Intracranial hemorrhage I60, I61, I62, I690, I691, I692, S064, S065, S066, S068 - Suicide attempt, self-harm T40 Poisoning by narcotics and psychodysleptics [hallucinogens] T41 Poisoning by anaesthetics and therapeutic gases T42 Poisoning by antiepileptic, sedative-hypnotic and antiparkinsonism drugs T43 Poisoning by psychotropic drugs, not elsewhere classified T54 Toxic effect of corrosive substances T60 Toxic effect of pesticides X60-X84 intentional self-harm - Myocardial infarction I21.9, I21.4, I21.0, I21.1, I21.2, I21.3, I22.0A, I22.0B, I22.0C, I22.8A,

PFIZER CONFIDENTIAL

			
I22.8B, I22.8C, I22.8D, I22.8E, I22.8F, I22.8G, I22.8H, I22.8I, I22.8, I22.9, I22.1A, I22.1B, I22.1C
 
 - Epilepsy/seizures G40.XX - Stroke 
 - Transient ischemic attack G459, I63, I693 - Hemorrhagic stroke I60, I61, I62, I690, I691, I692 - Ischemic stroke I63 
[NOTE] Hospitalization and CT or MRI codes such as brain CT or MRI procedure code for ischemic stroke and hemorrhagic stroke, or any CT or MRI for systemic embolism are also required for identification.
 
 * Brain CT HA441, HA451, HA461, HA471, HA851 * Brain MRI HE101, HE102, HE135, HE201, HE202, HE235, HE301, HE302, HE401, HE402, HE501, HE502, HE535 * Any CT or MRI or CT HA401-HA416, HA424, HA425, HA434, HA435, HA443-HA449, HA453, HA456-HA459, HA463-HA469, HA473-HA479, HA496, HA497, HA801, HA805, HA809, HA813, HA834, HA835, HA853, HA856, HA857-HA859, S852 * MRI HE103-HE142, HE203-HE234, HE236-HE241, HE303-HE334, HE403-HE434, HE430-HE434, HE503-HE534, HE536-HE541, HF101, HF102, HF104-HF107, HF201, HF202, HF305, HF306 
 - Hyponatremia 
 - will be identified by
--	--	--	---

			prescription codes for vasopressin receptor antagonists such as tolvaptan (drug code=616501ATB)

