**Study population**

Subjects who newly initiated antidepressant therapies between Jan 01, 2018 to Jun 30, 2019 in the Health Insurance Review and Service (HIRA) database

PFIZER CONFIDENTIAL

* Index date is the first prescription date of study drugs, including SSRIs, SNRIs, and other ADs during the intake period (Jan 01, 2018 to Jun 30, 2019).

Data source

The Korean HIRA claims data covers 97% of Korean population (about 50 million people) in the Korean National Health Insurance and 3% of Korean population in Medical Aid program.

HIRA claims database from January 01, 2017 to December 31, 2020 will be used for the analysis. It contains the data of universal health insurance system in Korea, wherein patient demographic information, inpatient and outpatient service use, pharmacy dispensing claims, and death can be obtained.

[figure not shown]
The main limitation of HIRA data is lack of clinical lab data and other clinical markers since it is a data collected for claims for reimbursement purpose.

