5.2 SAFETY ENDPOINTS

Adverse outcomes are primary endpoints in this study and they include the following categories defined by KCD-7 diagnosis codes and/or NHI procedure codes appearing in medical claims data after the index date.

- GI bleeding
I850, I983, K2211, K226, K228, K250, K252, K254, K256, K260, K262, K264, K266, K270, K272, K274, K276, K280, K282, K284, K286, K290, K3181, K5521, K625, K920, K921, K922
- Fractures
S02, S12, S22, S32, S42, S52, S62, S72, S82, S92, T02, T08, T10, T12, T14.2
- Falls
W00-W19
- Intracranial hemorrhage
I60, I61, I62, I690, I691, I692, S064, S065, S066, S068
- Suicide attempt, self-harm
T40 Poisoning by narcotics and psychodysleptics [hallucinogens]
T41 Poisoning by anaesthetics and therapeutic gases
T42 Poisoning by antiepileptic, sedative-hypnotic and antiparkinsonism drugs
T43 Poisoning by psychotropic drugs, not elsewhere classified
T54 Toxic effect of corrosive substances
T60 Toxic effect of pesticides
X60-X84 intentional self-harm
- Myocardial infarction
I21.9, I21.4, I21.0, I21.1, I21.2, I21.3, I22.0A, I22.0B, I22.0C, I22.8A, I22.8B, I22.8C, I22.8D, I22.8E, I22.8F, I22.8G, I22.8H, I22.8I, I22.8, I22.9, I22.1A, I22.1B, I22.1C
- Epilepsy/seizures
G40.XX
- Stroke
 - Transient ischemic attack
G459, I63, I693
 - Hemorrhagic stroke
I60, I61, I62, I690, I691, I692
 - Ischemic stroke
I63

[NOTE] Hospitalization and CT or MRI codes such as brain CT or MRI procedure code for ischemic stroke and hemorrhagic stroke, or any CT or MRI for systemic embolism are also required for identification.

- Brain CT
HA441, HA451, HA461, HA471, HA851
- Brain MRI
HE101, HE102, HE135, HE201, HE202, HE235, HE301, HE302, HE401, HE402, HE501, HE502, HE535
- Any CT or MRI or CT

HA401-HA416, HA424, HA425, HA434, HA435, HA443-HA449, HA453, HA456-HA459, HA463-HA469, HA473-HA479, HA496, HA497, HA801, HA805, HA809, HA813, HA834, HA835, HA853, HA856, HA857-HA859, S852

- MRI
HE103-HE142, HE203-HE234, HE236-HE241, HE303-HE334, HE403-HE434, HE430-HE434, HE503-HE534, HE536-HE541, HF101, HF102, HF104-HF107, HF201, HF202, HF305, HF306
- Hyponatremia
Will be identified by prescription codes for vasopressin receptor antagonists such as tolvaptan (drug code=616501ATB)

CC
I

[figure not shown]

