Recurrence	Primary outcome	HIRA Database	
Recurrence during the acute treatment phase was operationally defined as either one of the following being satisfied:
 
 1) inpatient episode with a diagnosis code in Table 1 2) inpatient episodes via the department of psychiatry or emergency medicine 3) inpatient episode via nursing hospital 4) emergency room visit with a diagnosis code in Table 1 5) suicide attempt identified by the following KCD-7 codes: 
 - T40 Poisoning by narcotics and psychodysleptics [hallucinogens] - T41 Poisoning by anaesthetics and therapeutic gases - T42 Poisoning by antiepileptic, sedative-hypnotic and antiparkinsonism drugs - T43 Poisoning by psychotropic drugs, not elsewhere classified - T54 Toxic effect of corrosive substances - T60 Toxic effect of pesticides - X60-X84 intentional self-harm 6) augmentation of the following non-AD drugs 
 - Antipsychotic amisulpride, aripiprazole, olanzapine, quetiapine, risperidone, perphenazine - Anticonvulsant carbamazepine, valproic acid, lamotrigine - Mood stabilizer lithium - Anxiolytic buspirone - Thyroid hormone levothyroxine, liothyronine 
Recurrence after the acute treatment phase was operationally defined as either one of the following being satisfied:
 
 1) ~6) the same as above 7) AD prescription after 30 days of drug holiday
Adverse outcomes	Primary outcome	HIRA Database	
The following known treatment related outcomes will be operationally defined by KCD-7 diagnosis codes and/or NHI procedure codes in medical claims
 
 - GI bleeding I850, I983, K2211, K226, K228, K250, K252, K254, K256, K260, K262, K264, K266, K270, K272, K274, K276, K280, K282, K284, K286, K290, K3181, K5521, K625, K920, K921, K922 - Fractures S02, S12, S22, S32, S42, S52, S62, S72, S82, S92, T02, T08, T10, T12, T14.2 - Falls W00-W19 - Intracranial hemorrhage

PFIZER CONFIDENTIAL

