		
I60, I61, I62, I690, I691, I692, S064, S065, S066, S068
 
- Suicide attempt, self-harm T40 Poisoning by narcotics and psychodysleptics [hallucinogens] T41 Poisoning by anaesthetics and therapeutic gases T42 Poisoning by antiepileptic, sedative-hypnotic and antiparkinsonism drugs T43 Poisoning by psychotropic drugs, not elsewhere classified T54 Toxic effect of corrosive substances T60 Toxic effect of pesticides X60-X84 intentional self-harm
 
- Myocardial infarction I21.9, I21.4, I21.0, I21.1, I21.2, I21.3, I22.0A, I22.0B, I22.0C, I22.8A, I22.8B, I22.8C, I22.8D, I22.8E, I22.8F, I22.8G, I22.8H, I22.8I, I22.8, I22.9, I22.1A, I22.1B, I22.1C
 
- Epilepsy/seizures G40.XX
 
- Stroke
 
 • Transient ischemic attack G459, I63, I693 • Hemorrhagic stroke I60, I61, I62, I690, I691, I692 • Ischemic stroke I63 
[NOTE] Hospitalization and CT or MRI codes such as brain CT or MRI procedure code for ischemic stroke and hemorrhagic stroke, or any CT or MRI for systemic embolism are also required for identification.
 
 • Brain CT HA441, HA451, HA461, HA471, HA851 • Brain MRI HE101, HE102, HE135, HE201, HE202, HE235, HE301, HE302, HE401, HE402, HE501, HE502, HE535 • Any CT or MRI or CT HA401-HA416, HA424, HA425, HA434, HA435, HA443-HA449, HA453, HA456-HA459, HA463-HA469, HA473-HA479, HA496, HA497, HA801, HA805, HA809, HA813, HA834, HA835, HA853, HA856, HA857-HA859, S852 • MRI HE103-HE142, HE203-HE234, HE236-HE241, HE303-HE334, HE403-HE434, HE430-HE434, HE503-HE534, HE536-HE541, HF101, HF102, HF104-HF107, HF201, HF202, HF305, HF306 
- Hyponatremia

--	--	--

PFIZER CONFIDENTIAL

			will be identified by prescription codes for vasopressin receptor antagonists such as tolvaptan (drug code=616501ATB)

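### Hyponatremia, a primary safety endpoint, is identified only by a vasopressin-antagonist prescription, so cases not given that drug count as event-free and other use of it counts as an event

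*SAP*

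**What the plan says.** SAP 5.2 gives these outcomes their status, "Adverse outcomes are primary endpoints in this study", and a general rule: they are "defined by KCD-7 diagnosis codes and/or NHI procedure codes appearing in medical claims data after the index date". Eight categories follow that rule by listing diagnosis codes: GI bleeding, fractures, falls, intracranial hemorrhage, self-harm, myocardial infarction, epilepsy and stroke. A note adds hospitalization and imaging requirements for ischemic and hemorrhagic stroke. The ninth, hyponatremia, lists no diagnosis or procedure code: "Will be identified by prescription codes for vasopressin receptor antagonists such as tolvaptan (drug code=616501ATB").

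The pattern is the same elsewhere. SAP Table 3 (section 5.4) says adverse outcomes are "operationally defined by KCD-7 diagnosis codes and/or NHI procedure codes in medical claims" and then gives the prescription-only entry. Protocol Table 3 (section 9.3) also relies on "prescription codes for vasopressin receptor antagonists such as tolvaptan (drug code=616501ATB"). Neither document gives a reason, a validation, an alternative definition or a sensitivity analysis. SAP 2.1 names as the main limitation of the database the "lack of clinical lab data and other clinical markers", but does not discuss what that means for this endpoint.

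**The concern.** The endpoint is called hyponatremia, but what is measured is dispensing of one drug class. Two errors follow from the wording. A patient with hyponatremia who is not given the drug cannot meet the definition, and with no laboratory data in the database nothing else will find the case. A patient given the drug for another reason meets the definition, because no accompanying diagnosis is required.

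Comparing the risk of these outcomes between individual antidepressants is part of the second primary objective (SAP 2.2). Protocol 9.7 plans time-to-event models, 95% confidence intervals and a 0.05 significance level. At stake are an absolute incidence that is too low, comparisons across 11 drugs based on few events, and ratios that may be distorted if prescribers' use of the drug differs between antidepressant groups. Missed cases also escape the rule in SAP 5.1 that periods with an identified adverse outcome are treated as non-adherent.

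**Working it through.** The documents give no hyponatremia rate, expected event count or power, so there is no planned figure to reproduce.

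**1. Effect on the estimate.** SAP 7.1 defines an incidence rate as patients with the event divided by observed time at risk. That sentence follows one naming only major bleeding and stroke, but the time-to-event models in Protocol 9.7 cover safety outcomes generally and work the same way. An undetected case adds time and no event.

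**2. Events captured.** All inputs are assumed: 20,000 patients per drug, true incidence 0.2% to 1%, and 1% to 20% of cases receiving the drug. Other uses of the drug are set to zero.

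Captured events = patients × incidence × capture.

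- Low end: 20,000 × 0.002 × 0.01 = 0.4.
- Middle: 20,000 × 0.005 × 0.05 = 5.
- High end: 20,000 × 0.01 × 0.20 = 40.

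**3. Precision.** For two drugs with E events each, the 95% limits are the ratio estimate divided and multiplied by exp(1.96 × √(2/E)).

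- E = 5: exp(1.96 × 0.632) = 3.45, so 0.29 to 3.45 times the estimate.
- E = 40: exp(1.96 × 0.224) = 1.55, so 0.65 to 1.55 times the estimate.
- E = 0.4: the approximation is not usable.

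**4. Power.** Further assumptions: true risk 0.5%, true risk ratio 1.5, two-sided 0.05, normal approximation for two proportions with pooled variance under the null. Observed risk = true risk × capture.

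| Capture | Events (20,000 per drug) | Power |
|---|---|---|
| 5% | 5 vs 7.5 | 0.11 |
| 20% | 20 vs 30 | 0.29 |
| 50% | 50 vs 75 | 0.61 |
| 100% | 100 vs 150 | 0.89 |

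The last row is a ceiling, not what a claims diagnosis code would deliver. The gain from a diagnosis code depends on its own capture, which is also unknown. The 5% row is rough because events are so few.

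**5. Bias in the ratio.** With no false positives, observed ratio = true ratio × (capture in drug A ÷ capture in drug B).

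- Equal capture: 1.5 × 1 = 1.5, unbiased.
- 5% vs 10%: 1.5 × 0.5 = 0.75.
- 10% vs 5%: 1.5 × 2 = 3.0.
- 20% vs 25%: 1.5 × 0.8 = 1.2.

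If the drug is also used for reasons unrelated to the antidepressant, those extra events pull the ratio toward 1.

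**The case against.** The strongest defence is that this is a deliberate, specific proxy. The entry is identical in three places, so the lead-in may simply be loosely worded, and no programmer would be misled. Protocol 9.9 warns of miscoding and of diagnoses entered to avoid denial of reimbursement, which is a reason to be wary of diagnosis codes. Objectives are exploratory, SAP section 3 lists no hypotheses, and confidence intervals will show any imprecision.

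Part of this stands. The lead-in allows diagnosis and/or procedure codes, so the departure is an inconsistency between a rule and one entry, not a breach of a strict diagnosis-code rule. Hyponatremia comes first in an illustrative list in SAP 2.2 and last in SAP 5.2, so position says nothing about priority. The capture share, on which the size depends, is assumed throughout.

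The rest does not remove the point. The miscoding caveat applies equally to the eight outcomes that do use diagnosis codes. Neither document claims specificity as the reason, and the wording 'such as' opens the list only to other drugs of the same class. A wide interval shows imprecision, but it shows neither under-ascertainment of incidence nor differential capture.

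**Conclusion.** The point holds. Followed as written, a primary safety endpoint leaves every hyponatremia case not given one drug class in the time at risk as event-free, counts use of that drug for other reasons as events, and departs from the section's own general rule. Absolute incidence is under-ascertained to the extent that missed cases outnumber false ones, and precision is lost. The size cannot be determined from the documents: on the assumed inputs, captured events range from 0.4 to 40 per drug.

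Three stronger readings are tempting but unsupported.

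- A reader might infer that the definition cannot detect any difference. At 40 events per drug the factor of 1.55 still leaves room to detect a large one.
- A reader might infer that the between-drug ratios are biased. They are if capture differs by drug. With equal capture and few false positives the ratio stays about right, and the documents give no evidence either way.
- A reader might infer that a diagnosis code would restore full capture. Without laboratory data it will miss cases too.

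**What to change.** 1. Define hyponatremia by its KCD-7 diagnosis code (to be confirmed), or the drug code. Add a claim requirement that limits rule-out coding, for example one inpatient or emergency claim or two outpatient claims, in line with the cohort's own diagnosis rule in SAP 4.1.
2. Report the prescription-only definition as a sensitivity analysis, named as vasopressin-antagonist-treated hyponatremia.
3. Amend the lead-in in SAP 5.2 and in both Tables 3 so that it includes drug codes.
4. State the remaining under-ascertainment, given no laboratory data, as a limitation.
5. Date and disclose the change. SAP section 1 records that the current amendment was made during data analysis, so redefining a primary endpoint now is a post hoc change. Note that it also alters which periods count as non-adherent under SAP 5.1.

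The cost is a revised query on claims of a type already used for the other outcomes, a rerun of this endpoint and of adherence, and the disclosure. The downside is that some miscoded or rule-out diagnoses will enter. The drug-only analysis does not bound that error, since it misses cases and may also admit other uses of the drug.

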5.4 COVARIATES

Table 3. List of Variable Categories

Variable	Role	Data source(s)	Operational definition
SSRIs	Exposure	HIRA Database	Prescription claims with a HIRA Drug Main Ingredient code for the following drugs defined in Table 2 will be used individually for each drug: Escitalopram, paroxetine, fluoxetine, sertraline
SNRIs	Exposure	HIRA Database	Prescription claims with a HIRA Drug Main Ingredient code for the following drugs defined in Table 2 will be used individually for each drug: Duloxetine, venlafaxine, desvenlafaxine
Other ADs	Exposure	HIRA Database	Prescription claims with a HIRA Drug Main Ingredient code for the following drugs defined in Table 2 will be used individually for each drug: Mirtazapine, tianeptine, vortioxetine, bupropion
Proportion of Antidepressants	Primary outcome	HIRA Database	
For each of 11 study drugs, the following proportions will be calculated
 
 1) Proportion out of total prescriptions in the first 90 days from the index date (acute treatment phase) 2) Proportion out of each gender in the first 90 days from the index date (acute treatment phase) 3) Proportion out of three age groups (≤ 20, 21-64, ≥ 65) in the first 90 days from the index date (acute treatment phase) 
Proportion out of 6 subgroups generated by 2 genders and 3 age groups in the first 90 days from the index date (acute treatment phase)

PFIZER CONFIDENTIAL

Dosage	Primary outcome	HIRA Database	
For each of 11 study drugs, the following dosages will be calculated: Initial dosage at the index date
 
The average dosage during the first 90 day period from the index date (acute treatment phase)

MPR (medication possession ratio)	Primary outcome	HIRA Database	For each of 11 study drugs, the MPR will be calculated by (Days of medication possession from the prescriptions filled in the 180 days) / (180 days + extra days of drug supply from the last prescription fill during the 180 days)
Persistence	Primary outcome	HIRA Database	
For each of 11 study drugs, the average length of treatment on the index drug during the first 180 day period (allowing 14 day permissible gap) will be calculated
 
Switching, combination, augmentation, discontinuation will terminate the persistent period

Discontinuation	Primary outcome	HIRA Database	For each of 11 study drugs chosen as index drug, the percentage of discontinuation in the first 90 days from the index date (acute treatment phase) will be measured (allowing 14 day permissible gap)
Adherence	Primary outcome	HIRA Database	
For each of 11 study drugs chosen as index drug, adherence will be measured by MPR and persistence during the first 90 day and 180 day period from the index date, respectively (acute treatment phase). MPR ≥ 0.75 and persistence ≥ 90 will be considered as adherence.
 
* For those period with any identified adverse outcome such as GI bleeding will be considered as non-adherent period

Drug utilization pattern in acute phase	Secondary outcome	HIRA Database	
During the first 90 day period starting from the index date, the following types of drug utilization pattern is recorded
 
- monotherapy (kept on the index medication)- switching (switched to other antidepressant)- combination (adding other antidepressant)- augmentation (adding other non-AD drug such as antipsychotic)
Drug utilization pattern in maintenance phase	Secondary outcome	HIRA Database	
During the second 90 day period (91 ~ 180 days) starting from the index date, the following types of drug utilization pattern is recorded
 
- choice of antidepressant- monotherapy (kept on the same medication)- switching (switched to other antidepressant)- combination (adding other antidepressant)- augmentation (adding other non-AD drug such as antipsychotic)

PFIZER CONFIDENTIAL

Recurrence	Primary outcome	HIRA Database	
Recurrence during the acute treatment phase was operationally defined as either one of the following being satisfied:
 
 1) inpatient episode with a diagnosis code in Table 1 2) inpatient episodes via the department of psychiatry or emergency medicine 3) inpatient episode via nursing hospital 4) emergency room visit with a diagnosis code in Table 1 5) suicide attempt identified by the following KCD-7 codes: 
 - T40 Poisoning by narcotics and psychodysleptics [hallucinogens] - T41 Poisoning by anaesthetics and therapeutic gases - T42 Poisoning by antiepileptic, sedative-hypnotic and antiparkinsonism drugs - T43 Poisoning by psychotropic drugs, not elsewhere classified - T54 Toxic effect of corrosive substances - T60 Toxic effect of pesticides - X60-X84 intentional self-harm 6) augmentation of the following non-AD drugs 
 - Antipsychotic amisulpride, aripiprazole, olanzapine, quetiapine, risperidone, perphenazine - Anticonvulsant carbamazepine, valproic acid, lamotrigine - Mood stabilizer lithium - Anxiolytic buspirone - Thyroid hormone levothyroxine, liothyronine 
Recurrence after the acute treatment phase was operationally defined as either one of the following being satisfied:
 
 1) ~6) the same as above 7) AD prescription after 30 days of drug holiday
Adverse outcomes	Primary outcome	HIRA Database	
The following known treatment related outcomes will be operationally defined by KCD-7 diagnosis codes and/or NHI procedure codes in medical claims
 
 - GI bleeding I850, I983, K2211, K226, K228, K250, K252, K254, K256, K260, K262, K264, K266, K270, K272, K274, K276, K280, K282, K284, K286, K290, K3181, K5521, K625, K920, K921, K922 - Fractures S02, S12, S22, S32, S42, S52, S62, S72, S82, S92, T02, T08, T10, T12, T14.2 - Falls W00-W19 - Intracranial hemorrhage

PFIZER CONFIDENTIAL

		
I60, I61, I62, I690, I691, I692, S064, S065, S066, S068
 
- Suicide attempt, self-harm T40 Poisoning by narcotics and psychodysleptics [hallucinogens] T41 Poisoning by anaesthetics and therapeutic gases T42 Poisoning by antiepileptic, sedative-hypnotic and antiparkinsonism drugs T43 Poisoning by psychotropic drugs, not elsewhere classified T54 Toxic effect of corrosive substances T60 Toxic effect of pesticides X60-X84 intentional self-harm
 
- Myocardial infarction I21.9, I21.4, I21.0, I21.1, I21.2, I21.3, I22.0A, I22.0B, I22.0C, I22.8A, I22.8B, I22.8C, I22.8D, I22.8E, I22.8F, I22.8G, I22.8H, I22.8I, I22.8, I22.9, I22.1A, I22.1B, I22.1C
 
- Epilepsy/seizures G40.XX
 
- Stroke
 
 • Transient ischemic attack G459, I63, I693 • Hemorrhagic stroke I60, I61, I62, I690, I691, I692 • Ischemic stroke I63 
[NOTE] Hospitalization and CT or MRI codes such as brain CT or MRI procedure code for ischemic stroke and hemorrhagic stroke, or any CT or MRI for systemic embolism are also required for identification.
 
 • Brain CT HA441, HA451, HA461, HA471, HA851 • Brain MRI HE101, HE102, HE135, HE201, HE202, HE235, HE301, HE302, HE401, HE402, HE501, HE502, HE535 • Any CT or MRI or CT HA401-HA416, HA424, HA425, HA434, HA435, HA443-HA449, HA453, HA456-HA459, HA463-HA469, HA473-HA479, HA496, HA497, HA801, HA805, HA809, HA813, HA834, HA835, HA853, HA856, HA857-HA859, S852 • MRI HE103-HE142, HE203-HE234, HE236-HE241, HE303-HE334, HE403-HE434, HE430-HE434, HE503-HE534, HE536-HE541, HF101, HF102, HF104-HF107, HF201, HF202, HF305, HF306 
- Hyponatremia

--	--	--

PFIZER CONFIDENTIAL

			will be identified by prescription codes for vasopressin receptor antagonists such as tolvaptan (drug code=616501ATB)
Comorbidities	Covariates	HIRA Database	
The following comorbidities which may affect the drug utilization patterns of antidepressants will be operationally defined using KCD-7 diagnosis codes in medical claims
 
 - Psychiatric comorbidities: panic disorder (F41.0), bipolar disorder (F31), PTSD (F43.1), acute stress (F43.0), personality disorder (F60-69), GAD (generalized anxiety disorder) (F41.1), adjustment disorder (F43.2), sleep disorder (F51), g470, f108), dementia (F00-F03, G30), OCD (obsessive compulsive disorder) ((F42), F429, F605, F428), substance related disorders (F10-19), schizophrenia (F20-29), eating disorder (F50), sexual dysfuntion (F52), mental retardation (F70-F79), developmental disorder (F80-F89), somatoform disorder F45, eating disorder F50 - Mild cognitive impairment (MCI): diagnosis code F06.7 along with a procedure code for neurocognitive function test FB001-FB060* - Charlson Comorbidity Index (CCI)
Non-pharmacologic treatments	Covariates	HIRA Database	
The following non-pharmacologic treatments which may affect antidepressant adherence and persistence/discontinuation will be defined using NHI procedure codes* in medical claims
 
 - Individual psychotherapy** NN012 intensive analytic NN013 intensive - Group psychotherapy NN021 general NN022 analytic NN023 psychodrama - Family psychotherapy NN031 individual NN032 group NN040 occupational or recreation therapy NN050 narcoticsynthesis - Electroconvulsive therapy NN071 simple ETC NN072 modified ETC - Continuous sleep treatment NN081 electro sleep treatment NN082 drug induced sleep treatment NN083 sleep treatment with anesthesia NN090 psychiatric rehabilitation NN100 psychiatric emergency treatment - Psychiatric social work NN111 individual history taking NN112 social work guidance NN113 social investigation

PFIZER CONFIDENTIAL

			
NN114 home visiting
 
* Since January 2018, new code system was employed for psychotherapy and expert advisor consensus will be used to align the new codes to the codes above
 
NN001-NN005 individual psychotherapy
 
NN061 Cognitive Behavioral Therapy-Individual
 
NN062 Cognitive Behavioral Therapy-Group
 
** NN011 supportive was excluded since it is more of a routine code used for majority of patients according to Ahn et al. (2012)¹³

Patient demographics and provider characteristics	Covariates	HIRA Database	
The following patient demographics and provider characteristics will be defined using medical claims
 
 - Age - Gender - Region of provider - Specialty of provider - Class of clinic/hospital
Number of visits	Covariates	HIRA Database	
The number of provider visits will be calculated from medical claims
 
 - Inpatients visits - Outpatient visits - Emergency room visits

